2.2 SECONDARY OBJECTIVES

Diabetes-related objectives:

1. Assess whether the drug has prolonged clinical efficacy.
2. Assess the effect of imatinib on selected secondary clinical outcomes.

Safety:

1. Determine the safety of imatinib in participants with T1DM, especially with respect to hepatic, bone marrow, cardiac, and cutaneous toxicity.

Mechanistic studies:

1. Characterize how imatinib alters general and diabetes-specific immune responses.
2. Gain a better understanding of the mechanism of action for imatinib in the maintenance of β -cell function and determine whether the loss of tolerance associated with this disease is reversed.
3. Assess effects of imatinib on insulin sensitivity.

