3. STUDY DESIGN**3.1 DESCRIPTION**

The study will be a multicenter, two-arm, double-blind, placebo-controlled, 2:1 randomly assigned, phase II clinical trial for individuals with recent-onset T1DM. The randomly assigned participants will receive either a 6-month course of imatinib or matching placebo tablets over a period of 26 weeks. Both treatment and placebo groups will undergo identical procedures and will be followed for 104 weeks. The primary endpoint, 2-hour C-peptide AUC measured at 52 weeks in response to a mixed-meal tolerance test (MMTT), will be measured at 52 weeks. Safety, diabetes control, β -cell function, and immune function will be assessed for 104 weeks. Both groups will receive intensive diabetes management. During the follow-up phase, participants will undergo serial clinical and immunologic assessments over the 104 week study period, and possible mechanisms of imatinib action will be assessed.

Initial enrollment will be for subjects ages 18-45, with the goal to lower the age down to 12 upon acceptable safety review and prospect of benefit for this initial older cohort. When the first 10 enrollees have completed their week 26 assessment, the safety data will be reviewed by a subcommittee that includes the protocol chairs, the medical monitor, the clinical trial physician, and the DSMB. If the review concludes that significant safety concerns have been identified, then no further enrollment will occur pending further data review and evaluation by the DSMB. If the DSMB decides that the study may proceed then the FDA will be notified of study progress and determine if further age restriction is necessary, or if enrollment may be opened for subjects down to age 12. After the first 21 subjects have completed 6 months, a further safety review will occur for the DSMB. Additionally, an interim efficacy assessment will be conducted for the DSMB and FDA. The FDA will again be apprised of study progress, with further consideration for lowering the age of enrollees to 12, if this has not occurred earlier. If and when the age is lowered, an identical review procedure will be followed when the first 10 pediatric participants (ages 12-17) have completed their week 26 assessment. If the review is satisfactory, then enrollment will continue for subjects ages 12-45 until the study is fully enrolled.

[figure not shown]

Figure 3. Study Schema

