5.2 DOSE MODIFICATION AND MANAGEMENT OF ADVERSE EVENTS

With the use of a relatively low dose of imatinib in an otherwise healthy population, we hope to minimize the nature and extent of AEs experienced. It is important to note here, as in section 1.4, that the AEs referenced below, if observed, will usually occur early in the course of treatment, are often self-limited, and do not usually require dose adjustment or discontinuation of imatinib. Nonetheless, the investigative team recognizes that cancer treatment is clearly different than the proposed elective clinical trial: side effects considered acceptable and tolerable in a cancer setting may not be considered in the same light for subjects in this study. Every effort will be made to carefully balance the intent to provide the maximum total prescribed dose of study drug to subjects, versus the discomfort and risk that may be accompanied with imatinib administration. The “art” of subject management in this study will be to minimize the number of subjects that drop out of the trial due to these side effects, working in close concert with the investigative team to either adjust study drug dose and/or provide symptomatic relief with concomitant medications. General guidelines are outlined below, but may need to be modified as deemed necessary, in consultation with the trial physicians and medical monitor. In general, when a dose reduction is required, the daily dose of imatinib or placebo will be halved: For adults, the dose will be reduced from

400 mg/day to 200 mg/day. Unless otherwise stated, the equivalent dose reduction in children will be from 260 mg/m²/day to 130 mg/m²/day. Investigators will be instructed to always round up to the nearest 50 mg increment for the half-dose dosage.

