5.2.8 Pregnancy

Site staff will regularly review the concerns regarding avoidance of pregnancy with participants during the course of the study, especially during the initial 6 months on therapy. Urine pregnancy tests will be conducted at baseline and every following visit while on study drug. Male participants are to use birth control at least 3 months after study drug discontinuation. If, despite these measures, a participant becomes pregnant, imatinib will be permanently discontinued and the participant will be counseled on potential risks to the fetus. Pregnancies of partners of male participants will also be followed.

Given the potential risk to the fetus, while on study drug/placebo, women of child-bearing potential, defined as all women physiologically capable of becoming pregnant, must agree to use highly effective methods of contraception.. This contraception should start 1 week or more prior to the start of study drug/placebo (noting that the terminal half-life of imatinib is approximately 18 hours, and 5 times this duration is 90 hours or ~4 days)) and continue during the subsequent 6 months of study drug/placebo dosing ***Highly effective contraception methods include:***

- Total abstinence (when this is in line with the preferred and usual lifestyle of the subject). Periodic abstinence (e.g., calendar, ovulation, symptothermal, post-ovulation methods) and withdrawal are not acceptable methods of contraception
- Female sterilization (have had surgical bilateral oophorectomy with or without hysterectomy) or tubal ligation at least six weeks before taking study treatment. In case of oophorectomy alone, only when the reproductive status of the woman has been confirmed by follow up hormone level assessment
- Male sterilization (at least 6 months prior to screening). For female subjects on the study the vasectomized male partner should be the sole partner for that subject
- Combination of any two of the following (a+b or a+c, or b+c):
 - a. Use of oral, injected or implanted hormonal methods of contraception or other forms of hormonal contraception that have comparable efficacy (failure rate <1%), for example hormone vaginal ring or transdermal hormone contraception
 - b. Placement of an intrauterine device (IUD) or intrauterine system (IUS)

- c. Barrier methods of contraception: Condom or Occlusive cap (diaphragm or cervical/vault caps) with spermicidal foam/gel/film/cream/vaginal suppository

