9.2 SECONDARY OUTCOMES AND ANALYSES

Additional analyses of the primary outcome will include:

- A log rank test of the difference in the hazard function between groups in the incidence of the loss of the 2 hour peak C-peptide < 0.2 pmol/ml on a semi-annual MMTT ¹⁹¹, and
- Longitudinal analyses using mixed effects models with a random intercept and slope of the C-peptide values over the post-treatment period, adjusted for the baseline level of C-peptide. The average intercept and slope will be compared between groups adjusting for age, gender and the baseline $\log(C\text{-peptide}+1)$.

Additional secondary objectives are to examine how imatinib affects the following:

- Mean area under the stimulated C-peptide curve (AUC) curve at 12 months
- Mean area under the stimulated C-peptide curve (AUC) over 4 hours at 24 months
- HbA1c levels over time
- Insulin dose (units/kg) over time
- Number of severe hypoglycemic events
- Number and severity of adverse events

The mean levels of quantitative variables (e.g. HbA1c and insulin dose) over all follow-up values will be compared between groups using a normal errors longitudinal analysis.

The prevalence of a binary characteristic (e.g. yes/no or positive/negative) at a single visit (e.g. a history of hypoglycemia during follow-up) will be assessed using a logistic regression model. The prevalence of a binary characteristic over time will be assessed using generalized estimating equations.

The rates of severe hypoglycemic events and severe adverse events will be computed (total number of events divided by total patient years of follow-up) and the rates compared using a Poisson regression model, allowing for over-dispersion using a quasi-likelihood model as appropriate. Tests of significance will employ a robust estimate of the variance.

The above analyses will also be conducted to adjust for age, gender, baseline $\log(C\text{-peptide}+1)$ and baseline HbA1c; and by race/ethnicity, as appropriate. Analyses will also be conducted to examine the effect of HLA or other genotype.

Analyses will also be conducted to assess heterogeneity of the effect of treatment group (the group difference) as a function of age, gender, baseline $\log(C\text{-peptide}+1)$ and baseline HbA1c; and by race/ethnicity and HLA or other genotype. Heterogeneity will

be assessed using a test of treatment group by covariate interaction in an appropriate regression model.

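### Severe adverse events are compared only over 104 weeks of follow-up although drug is taken for 26; adding a fixed on-treatment period would usually make the comparison more sensitive

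*Combined protocol and SAP*

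**What the plan says.** Section 9.2 defines one rate for severe adverse events. The rates of severe hypoglycemic events and "severe adverse events will be computed (total number of events divided by total patient years of follow-up"), and these are then "rates compared using a Poisson regression model, allowing for over-dispersion using a quasi-likelihood model as appropriate". No other person-time denominator appears in section 9.

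Under section 3.1, participants "receive either a 6-month course of imatinib or matching placebo tablets over a period of 26 weeks". The same section adds: "Both treatment and placebo groups will undergo identical procedures and will be followed for 104 weeks". Section 8.2 has adverse events assessed for the whole study, and the Schedule of Events (Appendix 1) lists them at every visit to week 104.

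On timing, section 5.2 says that the adverse events it covers "will usually occur early in the course of treatment, are often self-limited". Section 5.2.8 gives a clearance time when setting contraception timing, "noting that the terminal half-life of imatinib is approximately 18 hours", and takes five half-lives as about 4 days.

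The safety objective in section 2.2 is: "Determine the safety of imatinib in participants with T1DM, especially with respect to hepatic, bone marrow, cardiac, and cutaneous toxicity". Section 3.3.2 lists named adverse event categories by arm, plus the frequency and severity of all adverse events, and states no time window for any of them.

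**The concern.** Three quarters of the planned person-time falls after dosing ends. Events in those 78 weeks are mostly background and are expected at similar rates in both arms. Pooling them with the 26 drug weeks pulls the rate ratio towards 1 and spreads any drug-caused excess over four times the exposure that produced it. Participants who stop drug early are asked to stay in follow-up (sections 4.3 and 5.3), which adds further off-drug time.

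At stake is how the final report reads. A real on-drug excess of severe events could appear as no clear difference, and the reported excess per patient-year would understate the risk while taking the drug.

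**Working it through.** The documents state no event rate, event count or power for the safety comparison, so there is no figure of the plan's own to reproduce.

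**Inputs from the documents.** Treatment 26 weeks and follow-up 104 weeks (section 3.1); 2:1 allocation (section 6.2.1); 66 participants (section 9.4), taken here as the exact 2:1 split, 44 imatinib and 22 placebo.

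**Assumptions.** A constant background rate b per patient-year in both arms; an on-drug rate ratio R; an off-drug ratio of 1; full dosing, complete follow-up and no over-dispersion. No background rate is given, so b is varied.

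**Absolute excess.** On drug it is b(R − 1). Averaged over follow-up it is b(R − 1) × 26/104 = b(R − 1)/4, a four-fold cut. At b = 0.5 and R = 3 the excess is 1.00 per patient-year on drug and 0.25 over total follow-up.

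**Rate ratio.** The total-follow-up ratio is (26R + 78)/104 = (R + 3)/4.

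- R = 2: (52 + 78)/104 = 1.25
- R = 3: (78 + 78)/104 = 1.5
- R = 4: (104 + 78)/104 = 1.75

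Poisson regression works on the log ratio, where the shrinkage is smaller than four-fold. For R = 3 it is ln 3 / ln 1.5 = 2.7, and for R = 2 it is ln 2 / ln 1.25 = 3.1.

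**Expected events at b = 0.5, R = 3.** The 26-week window has 22 patient-years on imatinib and 11 on placebo, giving 22 × 0.5 × 3 = 33 and 11 × 0.5 = 5.5 events. Total follow-up has 88 and 44 patient-years, giving 33 + 66 × 0.5 = 66 and 44 × 0.5 = 22 events. The excess event count is the same in both; what total follow-up adds is background. The Wald z for the rate difference is therefore 2.97 on drug and 1.77 over total follow-up, a fall of 1.7-fold.

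**Power.** Exact conditional binomial test (imatinib share of exposure 2/3, one-sided 0.025), averaged over Poisson counts, for R = 3:

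| Assumed background per patient-year | Total follow-up | 26-week window |
|---|---|---|
| 1.0 | 64% | 97% |
| 0.5 | 35% | 72% |
| 0.2 | 13% | 26% |
| 0.1 | 6% | 5% |
| 0.05 | 1.7% | 0.1% |

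For R = 2 at 0.1 per year the figures are 2.7% and 0.5%; for R = 4 at 0.1 per year they are 12% and 15%.

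**Sensitivity to the off-drug background.** If the off-drug background is half the on-drug background (b = 0.5, R = 3), the total-follow-up ratio is 1.8 and power is 47%, against 72% in the window. If no off-drug events occur, the ratio and the test are the same under either denominator and only the absolute rate falls four-fold.

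**The case against.** A reader might infer that the whole safety comparison is diluted four-fold and that the safety objective is therefore poorly answered. The documents do not support that.

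- **Scale.** Four-fold applies to the absolute excess and, under a constant background, to R − 1. The planned Poisson comparison is affected less. Both arms share the same follow-up, so the test is not invalidated.
- **Other safety coverage.** Section 3.3.2 reports named adverse event categories and all adverse events by arm. Section 3.1 plans safety reviews when the first 10 enrollees complete week 26 and after 21 complete 6 months. Section 8.2 has the DSMB review events by arm about every three to six months, and section 3.7.2 sets stopping rules. These stand as safeguards, but they are monitoring or unwindowed listings; none is a final between-arm on-treatment comparison.
- **Background rate.** At 0.5 per patient-year, placebo participants would average one severe event each over two years. Section 5.2 describes an otherwise healthy population, so the true rate may be lower, and the gain disappears or reverses at about 0.1 or below for ratios of 2 to 3. This stands as a limit on the size of the benefit.
- **Off-drug ratio of 1.** The trial tests whether effects outlast dosing (sections 3.4 and 3.5), and the plan looks for later harm, such as growth at 12 months and urinalysis and prostate specific antigen to week 104. This is a good reason to keep the total-follow-up rate.
- **Replacing the main comparison.** A window ending at each participant's last dose would be cut short informatively, because sections 5.2 and 5.3 tie discontinuation to adverse events. This also stands and shapes the fix.

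**Conclusion.** The point holds as a cheap improvement. The only planned rate comparison for severe adverse events uses a denominator four times the treatment period, with no by-period analysis. If the excess is confined to the drug period, its absolute rate is understated four-fold, and under a constant background a true ratio of 3 is estimated as 1.5. The result is lost sensitivity in a valid comparison, with power roughly halved at assumed backgrounds of 0.2 to 0.5 per patient-year for an on-drug ratio of 3. The text and the four-fold arithmetic are certain. The size of the power loss is not, because it rests on assumed background rates and on an off-drug ratio of 1.

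**What to change.** In section 9.2, keep the total-follow-up rate and add a prespecified by-period comparison of severe adverse events, and of the section 3.3.2 safety categories, by randomised arm:

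- a fixed window of weeks 0–26 plus a short stated lag, with the person-time in that window as the denominator;
- a separate window from then to week 104, with its own person-time, so that delayed harm stays visible.

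Do not end the window at each participant's last dose in the main by-period analysis. Leave severe hypoglycemia on total follow-up, since section 3.3.2 lists major hypoglycemic events as an efficacy endpoint.

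The cost is SAP wording and one extra table. Adverse events and study drug dispensing are already recorded, so no new data are needed. Each period will hold fewer events, so its confidence intervals will be wider than those for the whole study, and at low event rates the on-treatment window may show little.

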9.3 ADDITIONAL OUTCOMES AND ANALYSES

Additional outcomes of interest include

- Change in autoantibody levels and/or B cell function
- Antigen specific and non-specific T and B cell subset enumeration and function
- Responses to vaccination (tetanus and killed flu)

The analyses of each outcome will be conducted using the methods for a quantitative outcome, binary outcome, or rate as described in Section 9.2 above.

9.4 SAMPLE SIZE AND POWER CALCULATIONS

The primary analysis will compare the difference between the treated group versus the placebo group in the levels of the 2 hour AUC-mean using the $\log(\text{mean C-peptide}+1)$ in an ANCOVA model adjusting for gender, baseline age, and baseline $\log(\text{C-peptide}+1)$. Estimates of $\log(\text{mean C-peptide}+1)$ and root mean square error (RMSE) in the placebo group were obtained from prior studies. Among subjects with baseline C-peptide > 0.2 pmol/ml and age ≤ 21 years, the mean $\log(\text{C-peptide} + 1)$ values is 0.306 with RMSE = 0.185.

The planning parameters for the protocol were based upon the inclusion of adults and children. Unfortunately, the FDA has declined the request to lower the age and, therefore, the study will only enroll adults at this time.

Hence, it is appropriate to revisit the design of the study in light of restricting the eligible population to be age 18 and over. In previous studies, it has shown the older a participant is, the lower the rate of C-peptide loss. This means that the current design of detecting a one-year C-peptide projected level 45% greater than expected on the control arm corresponds to an increase in C-peptide over the baseline value at enrollment, which is not practical. However, analyses completed after this study was initially designed indicate that the appropriate variance estimate to use for the sample size calculation should be smaller than what was used in the current design. This has the net effect of increasing the sensitivity of the trial to detecting an effect size smaller than the advertised value in the current design.

Using standard equations for the comparison of two means, a sample size of 40 Imatinib treated and 20 placebo treated subjects with complete data needed for the primary analysis, would provide power of 85% to detect a 0.35 increase in the mean $\log(\text{C-peptide} + 1)$ (0.306 vs. 0.445, which corresponds to 75% of the RMSE) in the experimental treatment group using a two-sample T- test at the 0.05 level (one-sided).

Assuming that 10% of the subjects will have missing data (one-year MMTT was not done or subject withdrew prior to the one-year assessment), the sample size goal for

this study is 66 subjects (46 + 22). Should the number with missing data exceed 10%, the study will enroll additional replacement subjects as needed.

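### Section 9.4's only power statement gives two different effects (0.35 and 0.139) and no adult mean or RMSE; the arm split and one column of the 9.5 table are also wrong

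*Combined protocol and SAP*

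**What the plan says.** Section 9.4 takes its planning values from prior studies: "Among subjects with baseline C-peptide > 0.2 pmol/ml and age ≤ 21 years", the mean log(C-peptide+1) is 0.306 with RMSE 0.185. It then reports that the FDA declined to lower the age limit, so "the study will only enroll adults at this time", and that the design has to be looked at again. In adults, it says, "detecting a one-year C-peptide projected level 45% greater than expected on the control arm corresponds to an increase in C-peptide over the baseline value", which it calls not practical. It adds that "the appropriate variance estimate to use for the sample size calculation should be smaller than what was used in the current design", with the net effect of "increasing the sensitivity of the trial to detecting an effect size smaller than the advertised value in the current design".

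The power statement follows. For 40 imatinib and 20 placebo participants with complete data, one-sided 0.05, the design "would provide power of 85% to detect a 0.35 increase in the mean" log(C-peptide+1), and the bracket explains this as "0.306 vs. 0.445, which corresponds to 75% of the RMSE". After a 10% allowance for missing data the goal is printed as "66 subjects (46 + 22"). The synopsis and the 9.5 table also use 66, and section 6.2.1 specifies 2:1 randomization.

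Section 9.5 gives conditional power at 21 of 66 patients, two-tailed alpha 0.05, with the effect defined as the mean difference over twice the SD, equal to 0.37. It quotes .26 (observed trend) and .74 (assumed effect) at an interim Z of 0.8. Its text also cites a treatment effect of about 30% at around 6 months.

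**The concern.** The effect in the sentence and the effect in its bracket cannot both be right, since 0.445 − 0.306 is 0.139, not 0.35. The bracket also keeps the planning values from younger subjects, and its ratio of 1.454 matches the 45% effect that the preceding paragraph rejects for adults. The section announces a redesign without printing the inputs of that redesign.

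This is the only power statement for the primary endpoint. If the trial is null, the result will be read against an 85% figure, and nobody can say from the plan which effect in adults that figure refers to. The assumed-effect column in 9.5, which supports the interim decision to move forward, rests on the same unreconciled effect.

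**Working it through.** **Inputs.** From 9.4: 40 + 20 evaluable; one-sided 0.05; placebo mean 0.306; treated mean 0.445; RMSE 0.185; stated increase 0.35; stated power 85%. From 6.2.1: 2:1 allocation. From 9.5: 21 of 66 patients at the interim, two-tailed 0.05, effect 2 × 0.37 = 0.74 SD.

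**1. Reproducing the 85%.** Two-sample t-test, df 58, noncentrality = (difference / RMSE) × √(40 × 20 / 60) = (difference / RMSE) × 3.651.

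- Difference 0.139: 0.139 / 0.185 = 0.751 RMSE, noncentrality 2.74, power **85.7%**. This matches both the 85% and the 75% of RMSE.
- Exactly 85% needs 0.743 RMSE, whatever the population.

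**2. Power under readings of 0.35, with the printed RMSE of 0.185.**

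| Reading | Difference | In RMSE units | Power |
|---|---|---|---|
| Absolute 0.35 | 0.350 | 1.892 | >99.9% |
| 35% of 0.306 (log scale) | 0.107 | 0.579 | 67% |
| 35% on the C-peptide scale (natural log assumed) | 0.088 | 0.477 | 53% |

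None gives 85%.

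**3. Could the bracket be the outdated part?** If 0.35 means 35% (an inference, as no percent sign is printed), the difference is 0.35 × 0.306 = 0.107. With an RMSE of about 0.143 this is 0.107 / 0.143 = 0.749 RMSE, and power is 85.5%. On that reading 0.445 and 0.185 are the leftovers. The 0.74 SD in 9.5 cannot decide between the two, because 0.139 / 0.185 = 0.751 and 0.107 / 0.143 = 0.749 fit it about equally well.

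**4. Dependence on the missing figures (assumed values).**

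- 35% of 0.306 with RMSE 0.17, 0.16, 0.15 or 0.143: power 74%, 78%, 82% or 85.5%.
- Largest RMSE that gives 85% for a 35% log-scale increase, 0.35 × mean / 0.743: 0.144 for mean 0.306; 0.165 for an assumed adult mean of 0.35; 0.188 for an assumed adult mean of 0.40.

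**5. Arm split.** 46 + 22 = 68. At 2:1, 66 is 44 + 22. Losing 10% of that leaves 39.6 + 19.8, with power 85.4% for 0.139 at RMSE 0.185.

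**6. The 9.5 table.** With t = 21/66, conditional power = Φ[(Z√t + θ(1 − t) − 1.96) / √(1 − t)]. For the observed trend θ = Z/√t. For the assumed effect θ = 0.74√(66/4) = 3.006 with equal arms, or 0.74√(66 × 2/9) = 2.834 at 2:1.

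| Interim Z | Printed, assumed effect | Equal arms | 2:1 |
|---|---|---|---|
| 0.0 | .54 | .543 | .487 |
| 0.4 | .65 | .649 | .595 |
| 0.8 | .74 | .744 | .696 |
| 1.2 | .82 | .823 | .784 |
| 1.6 | .89 | .885 | .855 |

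The observed-trend column reproduces (.009, .065, .256, .580, .856) and does not depend on allocation, which supports the formula and isolates the problem to the other column. If the effect were 35% of 0.306 at RMSE 0.185 (0.579 SD), conditional power at Z = 0.8 and 2:1 would be .502.

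**The case against.** The best defence is that the 85% is correct for 0.75 RMSE, and power for 0.75 RMSE is the same in any population. On that view only the translation into an adult C-peptide effect is missing, and sample size, test and conduct are unaffected. The arithmetic in this stands, and nothing here shows the trial to be underpowered. But that translation is what a reader needs, and the section itself says the old values do not suit adults.

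Second, reading 0.306 vs 0.445 as the rejected 45% effect depends on taking the ratio of log(x+1) values. If natural logs are assumed and the means back-transformed, they are 0.358 and 0.560, an increase of about 57%. This is a fair caution about scale. It does not rescue the bracket, because an effect larger than 45% is even harder to defend on the section's own reasoning.

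Third, the .70 holds only at the two-tailed 0.05 stated with the 9.5 table. At the one-sided 0.05 of 9.4 (critical value 1.645) and 2:1, the column would be .64/.73/.81/.88/.93, above the printed values. That condition stands. The mismatch of alpha between 9.4 and 9.5 is a separate matter that the same rerun should settle.

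Fourth, the only numerical interim criterion is Z of at least 0.8, so moving from .74 to .70 changes no printed threshold. The 30% effect at 6 months concerns a different time point and an untransformed scale, so it adds to the confusion but is not direct evidence of error. Both are fair limits on the consequence.

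**Conclusion.** The concern holds. The power sentence contradicts itself, and the documents do not settle which figure is out of date. The 85% follows only from the 0.139 contrast at RMSE 0.185, values taken from subjects aged 21 or under. At that RMSE, 0.35 gives over 99.9% as an absolute difference and 67% as a log-scale percentage. Power for the adults now enrolled cannot be computed from the plan, because the adult mean and the revised RMSE are not printed. It could still be 85%, but the plan does not show it.

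The linked errors are smaller and definite. The arm split is two patients over the stated total. The assumed-effect column in 9.5 is about 3 to 6 points too high for 2:1 allocation at the table's own effect size and two-tailed level. These are wrong figures that should be corrected; they do not undermine the primary analysis.

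**What to change.** In 9.4, print the adult placebo mean and the revised RMSE from the analyses the section describes as completed. State one effect three ways: as a difference in log(C-peptide+1), as a percentage with its scale named, and as a fraction of the RMSE. Restate the power of 40 + 20 for that effect, even if it is below 85%. Simply replacing 0.35 with 0.139 is not enough, because that restores the effect the section rejects. Change the arm split to 44 + 22 and keep the total of 66.

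In 9.5, recompute the assumed-effect column and the .74 in the text for the reconciled effect and 2:1 allocation. State which alpha applies, so that it agrees with 9.4; if the level changes, rerun the observed-trend column too.

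The cost is one rerun of the power calculation and of the table, plus wording changes. No patients are added and the primary analysis stays as it is. The stated figures may become somewhat less favourable.
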